- a) **Specific Aim 1: Collect preliminary data on the psychiatric outcomes of pregnant women with Bipolar Disorder who undergo a TDM protocol for lamotrigine.** Hypothesis: Women undergoing a TDM protocol for lamotrigine will have a low rate (defined as <30%) of psychiatric relapse. Psychiatric outcomes will be defined by clinician interview, the Edinburgh Postnatal Rating Scale (EPDS) and the Young Mania Rating Scale (YMRS).
- b) **Specific Aim 2: Collect adverse event data from pregnant women with Bipolar Disorder undergoing a TDM protocol for lamotrigine.** Adverse event data will be collected using the UKU side effect semi-structured interview and the Frequency, Intensity, and Burden of Side Effects Rating (FIBSER) scale.
- c) **Specific Aim 3: Collect preliminary data on the obstetrical outcomes of pregnant women with Bipolar Disorder who undergo a TDM protocol for lamotrigine.** Obstetrical outcomes will be defined by review of the delivery admission chart by an obstetrician using the Peripartum Events Scale (PES).
- d) **Specific Aim 4: Collect preliminary data on infant outcomes whose mothers underwent a TDM protocol for lamotrigine.** Pediatric outcomes will be defined by review of the infant delivery chart by a pediatrician and by a neurobehavioral assessment using the Neonatal Intensive Care Unit (NICU) Network Behavioral Scale (NNS).

3. Background:

Evidence indicates that serum levels of lamotrigine decrease by 200-250% across pregnancy¹⁹, and that the clearance of lamotrigine can be increased 10-fold across pregnancy in many but not all women²⁰. In the epilepsy literature, levels between 2.5 and 15 have been reported for therapeutic efficacy with higher levels correlated with increasing signs of toxicity²¹. In the epilepsy literature, there is a published protocol for lamotrigine management before, during, and after pregnancy²² for seizure control as follows:

- *Prior to pregnancy, adjust lamotrigine dose to minimum effective dose to attain clinical stability. Obtain a reference concentration (RC), preferably when the patient is not taking oral contraceptives.*
- *During pregnancy, monitor lamotrigine concentration every 4 weeks. If serum concentration falls below RC, increase lamotrigine dose by 20-25% and re-measure serum level after 4 additional weeks. If serum level does not fall below RC, maintain same dose but check level again in four weeks.*

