Lamotrigine Dosing Adjustments. At the time of study enrollment each participant will have a RC defined based on either 1) a pre-pregnancy serum level (for the current lamotrigine dosage) or 2) a serum level drawn at the time of enrollment. While we will preferentially use a pre-pregnancy RC since pregnancy hormone levels can affect lamotrigine levels, many psychiatrists do not routinely check lamotrigine levels and from a practical perspective we will obtain a lamotrigine at study entry to promote study participation and recruitment. Participants will be clinically well at the time of enrollment so that the serum level will be correlated with clinical stability. Lamotrigine levels will then be drawn monthly and the dose adjusted to maintain the RC. Specifically, if the monthly serum level is more than 0.5µg/mL lower than the RC, the dose will be adjusted by 20-25% and checked again at the next monthly visit. Higher levels than the RC are unlikely, since levels generally decrease across the course of pregnancy, but the dose will not be adjusted down unless there is a clinical indication (i.e. toxicity). Postpartum, all participants will be instructed to taper to the lamotrigine dose that was being taken at the time of the RC over the course of two weeks. While this does not follow the exact neurology, protocol described above (Background), we believe this approach makes sense since it will be more consistent and avoid the potential problem of toxicity. It also follows the recommendations of Clark et al²³.

Data Collection

a) **Maternal Psychiatric Outcomes:** We will monitor maternal psychiatric outcomes based on the EPDS, YMRS and clinical interview. The primary endpoint is the proportion of women who experience psychiatric relapse from the time of enrollment to 6 weeks postpartum. **Relapse** will be defined as one of the following: meeting SCID criteria for a Major Depressive Episode, meeting SCID criteria for a hypomanic or manic episode, development of high risk suicidal plan or attempt, or psychiatric hospitalization.

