b) **Maternal Adverse Event Outcomes:** Adverse events will be monitored by using a semi-structured interview, (the UKU side effects rating scale) at every visit as well as the self-rated Frequency, Intensity and Burden of Side Effects Rating scale (FIBSER). Adverse events will be considered as related to the TDM protocol if they were not present at baseline or worsened in severity and were noted after a change in dosing. A preliminary analysis will be conducted comparing adverse events in participants who underwent dose increases during pregnancy to those that did not (assuming there are participants who did not undergo dosage increase).

c) **Maternal Obstetrical Outcomes:** Maternal obstetrical outcomes will be extracted from the delivery admission chart which will be reviewed by the study obstetrician, [name]. The Perinatal Events Scale (PES) will be used to collect a majority of these outcomes including Past Obstetrics History, Medical Risk Factors, Obstetric Risk Factors, Progress in Labor, Method of Delivery and Complications. A preliminary analysis will be conducted comparing obstetrical outcomes in participants who underwent dose increases in pregnancy to those that did not (assuming there are participants who did not undergo dosage increase).

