d) **Newborn Outcomes:** Newborn outcomes will be extracted from the delivery admission chart which will be reviewed by the study pediatrician, [name]. We will use the infant outcomes portion of the Peripartum Events Scale (which includes Apgar scores and Infant Complications) and, in addition, collect infant weight, measurements, gestational age and need for medical interventions or NICU admission. A preliminary analysis will be conducted comparing infant outcomes for participants who underwent dose increases during pregnancy to those that did not (assuming there are participants who did not undergo dosage increase). All infants will also undergo a neurobehavioral assessment at weeks 2, 4 and 6 postpartum using the Neonatal Intensive Care Unit (NICU) Network Behavioral Scale (NNS). Our research assistant will receive training at the Brown Center for the Study of Children at Risk which has a standardized training on the use of NNS. The NNS will be used to identify any infant neurobehavioral effects of the TDM protocol. A preliminary analysis will be conducted comparing infant neurobehavioral outcomes for participants who underwent dose increases during pregnancy to those that did not (assuming there are participants who did not undergo dosage increase).

- b. **Study duration and number of study visits required of research participants.** Each subject will be seen approximately 12 times across the course of the study. We will attempt to recruit subjects who are less than 20 weeks pregnant and will plan for monthly study visits during pregnancy. Women and their infants will also be assessed after delivery at 1, 2, 4, and 6 weeks postpartum. We expect that most study visits will take place in the Women's Mood Disorders Center, however home visits by research assistants will be used if a participant cannot come to the Center (for example if a participant is on bedrest) to maintain participation and continuity.
- c. **Blinding, including justification for blinding or not blinding the trial, if applicable.** Not applicable. Subjects will be receiving the drug that is part of their usual care and we will be collecting pilot data.
- d. **Justification of why participants will not receive routine care or will have current therapy stopped.** Participants will undergo more clinical care than is currently routine in that they will be monitored on a monthly basis and their lamotrigine dosing adjusted as part of a TDM protocol.

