- e. **Justification for inclusion of a placebo or non-treatment group.** There will be no placebo or non-treatment group.

- f. **Definition of treatment failure or participant removal criteria.** Participants will be removed from the study if they meet criteria for Relapse as described above. Participants will also be removed if they are lost to follow-up or are noncompliant with the study protocol.
- g. **Description of what happens to participants receiving therapy when study ends or if a participant's participation in the study ends prematurely.** Participants will return for clinical care to their outpatient provider at the end of the study or if their participation ends prematurely.

5. Inclusion/Exclusion Criteria

Inclusion Criteria. Pregnant women with a history of Bipolar Disorder (Bipolar Disorder I, Bipolar Disorder II or Bipolar Disorder not otherwise specified) who are taking lamotrigine and who intend to continue lamotrigine through pregnancy will be enrolled. All participants must be in the first 20 weeks of pregnancy at the time of enrollment. All participants must also be on stable doses of lamotrigine (for the past 4 weeks), have an EPDS <13, a YMRS <12 and be judged by the study clinician to be clinically stable. Participants may be taking other psychiatric and nonpsychiatric medications.

Exclusion Criteria. Participants who have active suicidal ideation or who are clinically unstable will be excluded. Participants who are dependent on alcohol, marijuana or other substances in the 90 days prior to study entry will be excluded.

6. Drugs/ Substances/ Devices

- a. **The rationale for choosing the drug and dose or for choosing the device to be used.** Lamotrigine is an evidence-based treatment for Bipolar Disorder in pregnancy. The rationale for our TDM/dosing regimen is based on recommendations in the epilepsy literature. There is currently no established protocol for the dosing of these drugs in pregnant patients with Bipolar Disorder.
- b. **Justification and safety information if FDA approved drugs will be administered for non-FDA approved indications or if doses or routes of administration or participant populations are changed.** There are no drugs with FDA approval for the management of mood disorders in pregnancy. Therefore, we must use FDA approved drugs for non-FDA approved indications, a common clinical practice.

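### The adverse-event relatedness rule rests on time order alone, so the related-event count cannot be read as an effect of the TDM protocol

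*Protocol*

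**What the plan says.** The rule is in section 4.a, Data Collection b). An adverse event counts as related to the TDM protocol "if they were not present at baseline or worsened in severity and were noted after a change in dosing". No other part of the protocol adds a time limit, a direction of dose change, or an assessment of other causes.

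The parts of the protocol that decide how this rule behaves are:

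- **Baseline.** Section 5: "All participants must be in the first 20 weeks of pregnancy at the time of enrollment".
- **Dose changes in pregnancy.** Section 4.a, Lamotrigine Dosing Adjustments: when a monthly level falls more than 0.5 µg/mL under the reference concentration (RC), "the dose will be adjusted by 20-25% and checked again at the next monthly visit".
- **Dose reductions.** The same paragraph has every woman taper over two weeks after delivery to the dose she took when the RC was set. Section 8.b also provides for lowering the dose if side effects or toxicity appear.
- **Assessments.** The UKU interview and the FIBSER scale are used at every visit. Section 4.b: "Each subject will be seen approximately 12 times across the course of the study". Four of these visits are postpartum, at 1, 2, 4 and 6 weeks.
- **Use of the data.** Specific Aim 2 is to "Collect adverse event data from pregnant women with Bipolar Disorder undergoing a TDM protocol for lamotrigine". Section 7 plans to describe adverse events. Section 4.a b) also plans a preliminary comparison of women with and without dose increases. Section 4.e states that there is no untreated group.

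**The concern.** The attribution rule asks only whether a symptom came after a dose change and was absent or milder at baseline. In this population many symptoms arise or worsen after week 20 for reasons unrelated to the drug, and childbirth brings more. After a first increase, every such symptom at every later visit satisfies the rule as written, even if the dose has since been stable.

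The rule also merges two different safety questions. For a woman whose dose has risen, the postpartum taper is itself a change in dosing, and it coincides with delivery and recovery. Events that follow a higher dose and events that follow a falling dose get the same label.

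The protocol presents its safety data as groundwork for a later multisite randomized trial. A related-event count that ordinary pregnancy can largely generate could make the approach look harmful. It could also bury a real signal after an increase or after the taper.

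**Working it through.** The protocol states no adverse-event rate and no related calculation, so there is no figure to reproduce. The check has two parts.

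**1. Applying the rule to the schedule.** Take a woman whose dose is increased once in mid-pregnancy.

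- Later pregnancy visits: a new or worse symptom comes after a change, so it is related.
- Postpartum weeks 1 and 2: these fall within the two-week taper. A symptom of delivery or recovery is related, and nothing in the rule says whether the increase or the reduction is meant.
- Postpartum weeks 4 and 6: the taper should be complete and she is back on her RC dose. A symptom first noted here is still related.

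A woman whose dose never moves has no related event by construction, whatever she develops. So the label partly records whether and when the dose was changed.

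**2. Illustration of size.** Inputs from the protocol: about 12 visits, 4 of them postpartum, hence 12 − 4 = about 8 in pregnancy; target of 16 women retained. Input that is an assumption: a probability q per visit of a new or worse symptom not due to the drug, set at 5%, 10% and 20%. Visits are treated as independent and equally risky, and the true drug effect is set to zero.

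With k visits after the first dose change, the chance that a woman has at least one event labelled related is 1 − (1 − q)^k.

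- First change at visit 2: k = 12 − 2 = 10.
- First change at visit 8, the last pregnancy visit on this count: k = 12 − 8 = 4, which are the four postpartum visits.

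| Eligible visits | q = 5% | q = 10% | q = 20% |
|---|---|---|---|
| k = 10 | 1 − 0.95^10 = 40% | 1 − 0.90^10 = 65% | 1 − 0.80^10 = 89% |
| k = 4 | 1 − 0.95^4 = 19% | 1 − 0.90^4 = 34% | 1 − 0.80^4 = 59% |
| Only the next visit after each of 3 increases (k = 3) | 14% | 27% | 49% |

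If all 16 women had a dose change at the stated visit, the first row corresponds to about 6.4, 10.4 and 14.3 women, and the second to about 3.0, 5.5 and 9.4.

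The third row shows what a one-visit window achieves. It lowers the misattribution but leaves a substantial part of it. If doses rise every month, as the dosing rule allows, almost every pregnancy visit is a next visit and the window narrows little before delivery.

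**The case against.** The strongest defence is that nothing in the plan hangs on the label. Aim 2 is to collect adverse-event data, section 7 only describes them, and no related-event rate, threshold or decision is defined. All events are recorded at every visit, so the label discards nothing. This stands, and it limits the point to the related-event count.

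A reader might infer that the Aim 2 safety result is wrong as defined. The protocol contains no such result to be wrong. A reader might also infer that the rule manufactures a difference between women with and without dose increases. It does not: the planned comparison is of adverse events in general, so women without an increase contribute all of theirs. That comparison is even a partial check on background symptoms, although it is small, non-randomised and possibly empty.

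The protocol speaks of events related to the TDM protocol, not caused by the drug. Counting taper events is consistent with that, because the taper is part of the TDM protocol. This is fair, but it does not make a single combined count informative.

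It can also be said that the missing time limit is read from silence and that windows are often left to an analysis plan. The protocol, however, does not leave attribution open. It states an operative rule, and a rule without a limit applies without one.

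Finally, over-counting harm is a defensible leaning in a small pilot. That supports keeping the broad count, provided it is labelled for what it is.

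**Conclusion.** The point holds for the related-event count and no further. As written, the rule absorbs symptoms of advancing pregnancy, delivery and the postpartum period in any woman whose dose was ever changed. It also mixes events after increases with events after reductions. The resulting count shows temporal association and cannot be interpreted as an effect of the TDM protocol. The full adverse-event tabulation and the increase versus no-increase comparison remain usable.

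The direction of the error is upward. Its size cannot be computed from the protocol: the ranges of 40–89% with 10 eligible visits and 19–59% with 4 rest on assumed background rates of 5–20% per visit, independent visits and no drug effect. The upper range also needs an early first change and about 8 pregnancy visits; a woman enrolled near week 20 would have fewer.

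**What to change.** Amend section 4.a, Data Collection b) as follows:

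1. Compare severity with the visit at which the dose was changed, instead of with enrolment.
2. Report events first noted at the next visit after an increase separately from events first noted during or after the postpartum taper or any other dose reduction.
3. Have the study clinician record, for each event, whether pregnancy, delivery or another cause is a likely explanation.
4. Keep the broad count of events at any time after a change, labelled as temporal association only, so that late-onset effects stay visible.

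The cost is protocol wording plus one recorded judgement per event. UKU and FIBSER are already collected at every visit, and the timing of dose changes should be known. No dosing rule is touched.

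Two limits remain. A delayed effect appears only in the broad count. The window reduces misattribution without removing it (14%, 27% or 49% over three increases under the same assumptions), which is why the clinician's judgement is needed as well.

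### Comparing adverse events by whether a woman ever had a dose increase either dilutes a real rise after the increase or is uninformative by definition; for delivery and infant outcomes only a small gestational-age effect remains

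*Protocol*

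**What the plan says.** Protocol section 4, Data Collection b, sets the adverse-event comparison: "A preliminary analysis will be conducted comparing adverse events in participants who underwent dose increases during pregnancy to those that did not". Its only condition is "assuming there are participants who did not undergo dosage increase". The same split appears in item c, "comparing obstetrical outcomes in participants who underwent dose increases in pregnancy to those that did not", and in item d, "A preliminary analysis will be conducted comparing infant outcomes for participants who underwent dose increases during pregnancy to those that did not", and again in item d for the neurobehavioral examination.

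Three other statements bear on it.

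- Timing of collection (item b): "Adverse events will be monitored by using a semi-structured interview, (the UKU side effects rating scale) at every visit". The self-rated FIBSER is used as well.
- Timing of increases (section 4, Lamotrigine Dosing Adjustments): "Lamotrigine levels will then be drawn monthly and the dose adjusted to maintain the RC". A level more than 0.5 µg/mL below the reference concentration (RC) triggers the change. After delivery, "Postpartum, all participants will be instructed to taper to the lamotrigine dose that was being taken at the time of the RC".
- Relatedness (item b, just before the comparison sentence): an event counts as related to the monitoring protocol if it is new or worse than at baseline and was seen following a dose change. The comparison sentence does not say whether it is limited to related events.

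Item d also lists gestational age among the newborn data: "collect infant weight, measurements, gestational age and need for medical interventions or NICU admission".

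**The concern.** Whether a woman is in the increased group is settled during follow-up by her monthly levels. Women enter on a stable dose (section 5), so an increased woman always has some time on her original dose first. A comparison of whole participants assigns that time, and any events in it, to the increase. The effect is to shrink a real rise in side effects, which is the wrong direction for a safety description. Section 4a offers the safety data as groundwork for a later randomized trial, and these are the only between-group comparisons that the protocol names.

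Delivery and newborn outcomes occur after any increase in pregnancy, so nothing can be misassigned there in this way. A weaker link remains: a woman who delivers early has fewer monthly levels and so fewer chances of an increase. Gestational age then helps decide the group in which it is compared.

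**Working it through.** **The plan's own figure.** Section 4a recruits up to 20 women and allows 4 drop-outs: 20 − 4 = 16. This is reproduced, and 16 is used below. No power or effect size is given for the increase comparison.

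**Assumptions not in the documents.** Entry uniform over weeks 6 to 20 (section 5 sets only the upper limit); visits every 4 weeks after entry until delivery; 12% preterm; a 15% chance of an adverse event at each pregnancy visit; a chance h of a first increase at each level; the dose changes after the visit whose level triggers it. Each setting was simulated with 400,000 women.

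**Reading 1: all adverse events are compared.** Let s be the share of the increased group's pregnancy visits up to and including the triggering one, and RR the true ratio of per-visit event rates after and before the increase. The increased group's rate is a mix of the two, so the ever/never ratio is

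observed ratio = s + (1 − s) × RR = 1 + (1 − s)(RR − 1).

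For RR = 2 and all women retained:

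| Chance of a first increase per level | s | Observed ratio |
|---|---|---|
| 20% | 47.3% | 1.53 |
| 30% | 41.8% | 1.58 |
| 40% | 36.4% | 1.64 |
| 2% in a tenth of women, 40% in the rest | 36.7% | 1.63 |
| 2% in three tenths, 60% in the rest | 28.9% | 1.71 |
| 5% at week 6, rising 1 point a week | 53.7% | 1.46 |
| 10%, rising 3 points a week, entry level counted | 23.7% | 1.76 |
| 30%, entry in weeks 6 to 12 only | 38.7% | 1.61 |

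Removing women at relapse hardly changes s (41.9% at h = 30%). As rates at h = 30%: 0.42 × 15% + 0.58 × 30% = 23.7%; the simulation gives 23.8% against 15.0% in never-increased women. Classifying by visit returns 30.0% against 15.0%.

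The comparator is also thin. Of 16 women at h = 30%, about 2.1 are never increased if all are retained, with 11 visits between them (3.6 women and 13 visits if women leave at relapse). No such woman exists in 10% of trials (retained) or 2% (removed); at h = 40% the figures are 38% and 8%.

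**Reading 2: only related events are compared.** Events before the first increase drop out, so the dilution goes. But relatedness requires a preceding dose change. A never-increased woman has one in pregnancy only if her dose is lowered, so her related pregnancy events are close to zero by definition, and the contrast reflects the definition.

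**Obstetrical and infant outcomes.** With no drug effect and all women retained, preterm birth is 11.2% in increased and 17.5% in never-increased women at h = 30%. In 16 women that is 2.1 × (0.175 − 0.112) = 0.13, or about 0.1 birth. If needing an increase is largely a fixed trait (2% in three tenths of women, 60% in the rest), the figures are 11.9% and 12.7%.

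**The case against.** The strongest objection is that the protocol fixes only a group label. It does not state which events enter, over what window or with what denominator, and an analysis plan that is not shown may settle these. That stands in part: the dilution depends on Reading 1 and cannot be stated as certain. It does not rescue the comparison, because Reading 2 also fails, and the label itself is fixed in the protocol.

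It is also fair that the analyses are called preliminary, that section 4a disclaims a comparison group and that section 7 only describes these outcomes. In 16 women chance outweighs the dilution: it lowers a true 15-point gap to 8.7 points, while the standard deviation of the ever/never gap is about 13 points even with independent events. This limits the severity.

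A reader might infer more than the documents support:

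- **That the misassignment holds for every summary and every outcome.** It does not hold under the related-events reading, nor for delivery and newborn outcomes.
- **That the split creates a false adverse-event signal.** With no drug effect the per-visit rates are 15.0% in both groups. A large gap (59.7% against 43.0%) needs both an any-event proportion, which the protocol does not name, and removal at relapse.
- **That late entry biases in a known direction.** The direction reverses if the chance of an increase rises steeply with gestation.
- **That increases will look clearly protective against preterm birth.** The effect is a fraction of one birth, and near zero under a fixed trait. Section 3 says that the large clearance change occurs in many but not all women, which lends that setting some support.

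**Conclusion.** The concern holds in limited form. As the adverse-event sentence reads, a true ratio of 2.0 would appear as about 1.6, with a range of about 1.5 to 1.8. The size rests on assumed chances of an increase and on a hypothetical doubling. The existence of visits before the increase follows from the protocol's own procedures. On the narrower related-events reading the comparison is uninformative for a different reason. For obstetrical and infant outcomes the only issue is the small dependence of the group on gestational age at delivery. The fault is a biased or empty description, not a false-positive test. Severity is minor to moderate.

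**What to change.** **Adverse events.** Replace the ever/never comparison with new or worsened UKU and FIBSER events per pregnancy visit. Count visits up to and including the one whose level triggers the first increase as unexposed, and later pregnancy visits as exposed. Tabulate by gestational period and report postpartum visits separately, since the dose is then being tapered. Keep it descriptive.

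The tabulation by period is needed because exposed visits come later. If the event rate rises from 10% to 20% over gestation with no drug effect, crude rates are 16.8% exposed and 14.3% unexposed, but within periods they differ by less than 1 point.

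**Obstetrical and infant outcomes.** Show the number of levels and gestational age at entry and at delivery by group, and do not read differences in gestational age or preterm birth as effects of the increase.

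**Cost.** Analysis wording and a little more work; the ratings, levels and dose changes are already collected. Cells are small: in 16 women at h = 30%, about 3 exposed and 17 unexposed visits before week 20, 12 to 14 and 17 to 18 in weeks 20 to 28, and 26 to 32 and 9 to 11 later. Visits within a woman are not independent, so no gain in precision is claimed.

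**Separately,** section 4f removes women who meet the relapse definition, while section 8b (Psychiatric Urgency/Emergency) keeps women who are psychiatrically ill but not at risk of harm in all study visits. The second may be meant for illness short of relapse. The two should be reconciled so that it is clear whether women who relapse stay in follow-up.

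### The dose-increase comparisons for adverse events, obstetric and infant outcomes rest on a no-increase group that is likely to be small and may be empty, and no graded fallback is named

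*Protocol*

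**What the plan says.** Section 4.a, Data Collection, sets the same two-group contrast four times. For maternal side effects it is "comparing adverse events in participants who underwent dose increases during pregnancy to those that did not". For delivery outcomes it is "comparing obstetrical outcomes in participants who underwent dose increases in pregnancy to those that did not". For newborns it is "comparing infant outcomes for participants who underwent dose increases during pregnancy to those that did not (assuming there are participants who did not undergo dosage" (the condition ends on the word increase), and the neurobehavioural examination gets the same comparison. Each time the text makes the analysis conditional on the second group existing, and calls it preliminary. It does not say what will be done if the group is missing or holds one or two women.

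Membership of the groups follows from the dosing rule in section 4.a: "if the monthly serum level is more than 0.5µg/mL lower than the RC, the dose will be adjusted by 20-25" per cent. I read adjusted as increased. The same paragraph adds: "Higher levels than the RC are unlikely, since levels generally decrease across the course of pregnancy". Section 3 states that "the clearance of lamotrigine can be increased 10-fold across pregnancy in many but not all women". The RC is either a pre-pregnancy level or "a serum level drawn at the time of enrollment", and section 5 allows enrolment up to 20 weeks.

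Two further places bear on the point. Data Collection b) attributes an adverse event to the protocol when it is new or worse than at baseline and follows a dose change. Section 7 promises only description of adverse events and of obstetric and infant outcomes.

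**The concern.** A woman counts as increased after a single qualifying level at any monthly visit. With levels expected to fall and a small absolute trigger, the rule that defines the groups also tends to empty one of them. The protocol concedes this but offers no alternative.

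The split is also coarse. A woman with one step and a woman with several steps fall in the same group, although the size of the dose rise is the quantity of interest for safety. Section 8 names newborn toxicity from increased dosing as a possible risk to be monitored, and Data Collection d) gives the neurobehavioural examination the task of detecting effects of the protocol on the infant. If the no-increase group holds very few women, the planned comparison can say almost nothing on that question.

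**Working it through.** **Sample size.** Section 4.a recruits 20 and allows 4 drop-outs: 20 − 4 = 16. This reproduces. No power, error rate or group split is stated for the dose-increase comparisons.

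**How small a fall triggers an increase.** Required relative fall = 0.5 / RC. Section 3 cites levels of 2.5 to 15 from the epilepsy literature, without a unit; I take µg/mL.
- RC 2.5: 0.5/2.5 = 20%
- RC 5: 10%
- RC 10: 5%
- RC 15: 3.3%

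**How low an RC must be to escape.** Smallest RC that triggers = 0.5 / (fractional fall). Section 3 says that "serum levels of lamotrigine decrease by 200-250% across pregnancy", which cannot be a percentage fall. I read it, as an assumption, as a 2- to 3.5-fold fall, that is 50% to 71%.
- 50% fall: 0.5/0.50 = 1.0 µg/mL
- 71% fall: 0.5/0.714 = 0.70 µg/mL
- 10-fold clearance rise at constant dose (90% fall): 0.5/0.90 = 0.56 µg/mL

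A woman who has the described fall triggers unless her RC is about 1 µg/mL or lower. A woman with an RC of 0.5 or less can never trigger.

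**Size of the no-increase group.** Let q be the share of women never increased. The documents do not give q, so I show an assumed range. With n = 16 and independent women, expected size = 16q, P(none) = (1 − q)^16, and P(2 or fewer) is the binomial sum over 0, 1 and 2.

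| q | Expected | P(none) | P(2 or fewer) |
|---|---|---|---|
| 5% | 0.8 | 44% | 96% |
| 10% | 1.6 | 19% | 79% |
| 20% | 3.2 | 3% | 35% |
| 30% | 4.8 | 0.3% | 10% |
| 40% | 6.4 | <0.1% | 2% |

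**What a small group can show.** At 1 versus 15 the smallest two-sided Fisher p-value is 1/16 = 0.0625. For illustration, take event rates of 10% without and 50% with an increase, and a two-sided 0.05 level (neither is in the protocol). Exact power is then 0% at 1 versus 15, 0.5% at 2 versus 14, 3.4% at 3 versus 13, 4.9% at 4 versus 12, and 22% even at 8 versus 8.

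**What the split pools.** About 12 visits (section 4.b) less 4 postpartum leaves about 8 in pregnancy. If the first sets the RC, 7 draws can trigger. One 20% step gives 1.20 times the RC dose; seven 25% steps give 1.25^7 = 4.77 times. The latter is an upper limit. A woman enrolled near 20 weeks has about 4 to 5 later draws, and four 25% steps give 1.25^4 = 2.44 times.

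**The case against.** The strongest reply is that the protocol already discloses the limitation. The comparisons are preliminary and conditional, an exploratory fallback is often left to a statistical analysis plan, and nothing in the protocol forbids a graded description. That stands, and it limits the severity. It does not remove the point, because the protocol itself chose this contrast and repeated it four times.

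A reader might infer more than the documents support:
- **That the no-increase group will be nearly or wholly empty.** This is not shown. The share is not stated, section 3 says many but not all women, an RC drawn as late as 20 weeks may follow part of the fall, no minimum RC is set, and women removed early under section 4.f may leave before any increase. At 30% to 40% never increased, 5 or 6 of 16 women would be in the group.
- **That Aims 2 to 4 lose their only internal contrast.** This is wrong for Aim 2, which has the comparison with baseline after a dose change. It is fair for Aims 3 and 4.
- **That the aims fail without the contrast.** They are worded as collecting data, and section 4.a openly chooses to have no comparison group.

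There is also a sound objection to one obvious remedy. The ratio of the last dose before delivery to the RC dose grows with time to delivery. Preterm birth cuts off dose steps, while gestational age and infant weight are outcomes, so that ratio could make higher dosing look protective. Printing gestational age beside it would not cure this. In addition, dose is raised to hold the level at the RC, so any dose ratio partly tracks the woman's clearance.

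**Conclusion.** The point holds as a minor one. Under the protocol's own trigger and expected fall, the no-increase group is likely to be small and may be empty: 0.8 to 6.4 of 16 women for an assumed 5% to 40%, with the chance of none running from 44% to below 0.1%. At one to four women the split is close to uninformative under the illustrative event rates. For obstetric and infant outcomes nothing else inside the study relates outcome to dosing.

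The conclusion rests on the assumed range for q, on independence between women, and on reading the cited levels as µg/mL. The gain from a graded measure cannot be computed, because the documents give no distribution of dose steps. Such a measure would remain estimable with an empty no-increase group, provided that women differ in the number of steps.

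**What to change.** In section 4.a, Data Collection b), c) and d):

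- Keep the yes/no comparison where both groups exist, and say that the no-increase group may be very small or empty.
- For obstetric, infant and neurobehavioural outcomes, add a descriptive analysis (scatter plot and rank correlation) against the ratio of current dose to RC dose at a fixed gestational age that all or nearly all women reach. Do not use the last dose before delivery.
- For adverse events, use the ratio at each visit, beside the existing comparison with baseline.
- Show RC source and gestational age at enrolment with these results, and label them exploratory.

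Separately, the percentage fall quoted in section 3 should be restated in a form that is arithmetically possible.

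The cost is a change of analysis wording and a little more analysis work. That the doses are on record is an inference, but a safe one: study staff adjust the dose monthly, and the postpartum taper returns each woman to her dose at the RC, so both parts of the ratio must be known. Women who deliver before the fixed gestation have no value and should be listed separately. No dosing rule changes.
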